### 6.1.1 Gynecological Examination

Patients will have gynecological examinations by the Investigator or authorized designee on Day(s) 0 and 7; or Day(s) 0, 7, and 14 if receiving prolonged treatment, in order to assess vulvovaginal signs of erythema, edema, and excoriation. During the examinations, patients will also be asked about any vulvovaginal symptoms of itching, burning, and irritation.

NOTE: The Investigator will always assess *vulvovaginal signs* of erythema, edema, and excoriation. *Vulvovaginal symptoms* of itching, burning, and irritation will always be assessed by patients themselves and asked about by the Investigator at site visits.

### 6.1.2 Patient Questionnaire

The questionnaire can be found in Appendix 1 in the CIP.

The Clinical Trial Unit will call the patients on Day(s) 4, 14 and 35; or Day(s) 4, 11, 21, and 42 if receiving prolonged treatment; and ask questions from the patient questionnaire relating to vulvovaginal symptoms (itching, burning, or irritation), usability, concomitant medications, and AEs, if any.

Questions from *Section 1* in the patient questionnaire relating to vulvovaginal symptoms of itching, burning, and irritation will be asked to patients over telephone on Day(s) 4, 14, and 35; or Day(s) 4, 11, 21, and 42 if receiving prolonged treatment. A recurrence question will be asked to patients at Days(s) 14 and 35 if not receiving prolonged treatment and at Days(s) 21 and 42 if receiving prolonged treatment.

Questions from *Section 2* in the patient questionnaire relating to usability in will be asked to patients on Day 7, and Day 14 if receiving prolonged treatment.

Questions from *Section 3* and *Section 4* in the patient questionnaire relating to concomitant medications and AEs, respectively, will be asked to patients at each visit/telephone contact.

## **6.2 Safety and tolerability assessments**

The below will constitute the local tolerability and safety assessments:

- Adverse events and Serious adverse events (SAEs), and
- Rate of withdrawals from the study and/or the study treatment.

# **7 Method of analysis**

---

## **7.1 General**

All statistical analyses will be performed in accordance with the ICH E9 guideline for Statistical Principles for Clinical Trials (1), using SAS® (Version 9.4 or higher, SAS Institute Inc., Cary, NC, USA).

### **7.1.1 Presentation of results**

If applicable, results will be presented together with the unit.

Continuous data will be summarised using descriptive statistics, and the following parameters will be reported:

- number of patients with evaluable observations and missing observations
- arithmetic mean and standard deviation
- median
- first and third quartiles
- minimum and maximum.

Categorical data will be presented using absolute frequency and percentage. When the absolute frequency is zero, the percentage will not be presented. Unless stated otherwise, the denominator for percentage calculations will be the total number of patients in the applicable analysis set, including patients with missing data. For variables with missing values, the number and percentage of patients with missing values will be presented.

Statistical testing will be performed using an overall significance level of 5%. The primary endpoint analysis will be based on one-sided testing, whereas the secondary endpoints analyses will be based on two-sided testing. Corresponding confidence intervals will be presented. See [Section 7.9](#) below for further information.

Data will be presented using an appropriate number of decimal places, to ensure that undue precision is not implied (e.g. the number of decimals should not exceed the accuracy of the measuring instrument). Raw data will be presented with the same number of decimals as collected, and derived data with an appropriate number of decimals based on general practice, mathematical rationale or scientific rationale.

Minimum and maximum values will be presented with the same number of decimals as the analysed variable and the other descriptive statistics will be presented with one decimal more. Percentages and proportions will be presented with one decimal. Confidence interval bounds will be presented with the same number of decimals as the corresponding point estimate, and p-values will be presented with 4 decimals or as '<.0001'.

Mock tables and graphs are presented in the Data Display Plan (DDP), which is a supplementary document to this analysis plan. Individual patient data listings will be presented according to the ICH E3 guideline for Structure and Content of Clinical Study Reports (2), unless stated otherwise.

#### 7.1.2 *Baseline*

Unless stated otherwise, the baseline value for a parameter is defined as the last non-missing value before the first self-administration of the study treatment by the patient. The first self-administration is to be performed on the same day as the first study visit (Day 0), after the study visit.

#### 7.1.3 *Analysis relative day*

The analysis relative day for an assessment/value is defined as the time in days from the date of first administration of treatment to the date of the assessment. The date of first administration of treatment is considered as day 0.

#### 7.1.4 *Analysis visit*

An analysis visit is defined as a categorical variable used to classify values within an analysis variable into temporal or conceptual groups used for analyses.

The visits as defined in the case report form, CRF, will be used as analysis visits.

In general, data from unscheduled visits will be presented in data listings only and not included in analysis or summary tables. An exception to this is data used to confirm eligibility in association with screening or randomisation where the last assessment will be considered in summaries of screening data.

#### 7.1.5 *Handling of missing data*

The statistical analysis will be based on the observed data, i.e. no imputation is planned. In case of one or more missing value(s) among the 6 items included in the calculation of the CVVS score, the CVVS score will remain missing. In case of one or more missing symptom value(s) in the 3 vulvovaginal symptom items (itching, burning, and irritation), the sum of the 3 vulvovaginal symptoms scores will be set to missing. See also [Sections 8.6 and 8.7](#) below.

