### 5.1 *Sample size*

Assuming the true cure rate is equal to 70 %, 22 patients are needed to obtain 90 % chance (90 % power) to show that the one-sided 95 % CI for the observed cure rate is above 40 %. To compensate for a small number of non-evaluable patients, 24 patients will be included.

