### 7.2.1 *Full analysis set*

Full Analysis Set (FAS): This is the primary population and comprises all patients entering the study and having received at least 1 dose of study treatment. Analyses of clinical performance will be performed against this population.

In addition to this, two sub-populations based on this FAS will be formed: “FAS (For patients not receiving prolonged treatment)”, and “FAS (For patients receiving prolonged treatment)”.

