### 7.2.2 *Per-protocol analysis sets*

Per Protocol (PP) Population 1 (PPAS Clinical Cure) - This will include all FAS patients without any major protocol deviation, i.e. patients who have completed the study and sufficiently complied with the study protocol, have available primary endpoint data and have received the study treatment according to protocol. The final definition of a major protocol deviation will be decided and defined at the clean file meeting and documented in the clean file report. If a relevant number of patients are excluded from the PP population, then the analysis of the primary clinical performance endpoint will be provided for the PP population. The main purpose with this analysis set is to analyse the primary endpoint, i.e. Clinical Cure.

Per Protocol (PP) Population 2 (PPAS Recurrence) - In addition to what was specified in the CIP, a second Per-protocol analysis set will be defined with the main purpose of analysing recurrence. The rationale for this is that the different recurrence rate analyses are regarded as important to also perform using a “per protocol” approach. The main purpose with this per protocol dataset is thus to analyse Recurrence. This population will constitute a sub-population from PP population 1 defined

above, and will be defined in similarity with this population, but instead based on the secondary recurrence rate endpoints. The final definition of a major protocol deviation with respect to these secondary endpoints, will be decided and defined at the clean file meeting and documented in the clean file report.

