### 7.9.1 Primary endpoints

- Clinical performance endpoint: Clinical cure rate on Day 7 will be calculated and presented together with a one-sided 95 % confidence interval based on the exact binomial distribution (Clopper-Pearson).
- Clinical safety endpoint: Safety and tolerability will be assessed according to [Section 7.10.2](#).

The primary clinical performance endpoint is the Clinical cure rate on Day 7, where clinical cure is defined as the absence of signs and symptoms of VVC in terms of having a composite vulvovaginal signs-and-symptoms (CVVS) score equal to or below 3, see [Section 3.1.1](#) above. The primary performance objective of the trial is to show that the Clinical cure rate is above 40 %, *i.e.* to show that the lower limit of the one-sided 95 % CI for the observed cure rate is above 40 %.

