### 7.9.4 *Sensitivity analyses of the primary clinical performance endpoint*

In addition to what is stated in the CIP, a sensitivity analysis is added in the analysis of the primary clinical performance endpoint. In this, patients responding “Negative” to the eCRF variable “Vaginal swab culture result”, [see Section 7.10.3](#) below, will be excluded.

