#### 8.5 Clinical cure rate

Clinical cure rate is based on a binary variable, where a clinically cured patient is

- Defined as the absence of signs and symptoms of VVC in terms of having a composite vulvovaginal signs-and-symptoms (CVVS) score equal to or below 3.
  - Each of the following 6 vulvovaginal signs and symptoms will be individually scored using the scoring scale below and then added together to determine the CVVS score.
    - Vulvovaginal signs: erythema, edema, or excoriation
    - Vulvovaginal symptoms: itching, burning, or irritation
  - Scoring Scale: each score should be objectively defined.
    - 0 = none (absent)
    - 1 = mild (slight)
    - 2 = moderate (definitely present)
    - 3 = severe (marked, intense)

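### The SAP does not settle whether a FAS patient without a Day 7 CVVS counts in the primary cure-rate denominator, and one such patient can decide the result

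*SAP*

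**What the plan says.** - **Analysis set.** The primary set is the FAS, which "comprises all patients entering the study and having received at least 1 dose of study treatment" (SAP 7.2.1). A Day 7 score is not required. The per-protocol set does require it: its patients must "have available primary endpoint data and have received the study treatment according to protocol" (SAP 7.2.2). The plan therefore foresees FAS patients without primary endpoint data.
- **Denominator default.** Unless stated otherwise, "the denominator for percentage calculations will be the total number of patients in the applicable analysis set, including patients with missing data" (SAP 7.1.1).
- **Missing data.** "The statistical analysis will be based on the observed data, i.e. no imputation is planned" (SAP 7.1.5). If any of the six items is missing, the CVVS is missing. This section points on to SAP 8.6 and 8.7, but not to 8.5, which defines cure.
- **Sample size.** 22 patients are needed, and "To compensate for a small number of non-evaluable patients, 24 patients will be included" (SAP 5.1; same text in protocol 9.3).
- **Primary analysis.** "Clinical cure rate on Day 7 will be calculated and presented together with a one-sided 95 % confidence interval" (SAP 7.9.1). Success means a lower limit above 40%. Cure is defined "in terms of having a composite vulvovaginal signs-and-symptoms (CVVS) score equal to or below 3" (SAP 8.5). Neither section names a denominator or gives a status to a missing score.
- **Bias.** Protocol section 9 says that if missing data become an issue, steps will be taken to reduce bias or to push it in the conservative direction. The SAP names no such step.
- **Sensitivity analysis.** "In addition to what is stated in the CIP, a sensitivity analysis is added in the analysis of the primary clinical performance endpoint" (SAP 7.9.4). It removes culture-negative patients and does not address missing scores.

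**The concern.** Take a FAS patient who has no Day 7 CVVS because she withdrew, missed the visit or has an unscored item. SAP 7.1.1 keeps her in the denominator, where she has the effect of a non-cure. SAP 7.1.5 and the allowance for non-evaluable patients suggest that she drops out of the calculation. The plan does not say which applies to the cure rate, its interval and the test against 40%.

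Two things are at stake. With 24 patients, a single case can move the lower limit across 40%, and in an open-label, single-arm trial the reading could be chosen with outcomes known. Also, if patients who leave in the first week tend to be those who are not improving, dropping them raises the cure rate.

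A smaller gap sits beside this. SAP 8.5 rests on the CVVS alone, so a patient who took an antifungal before the Day 7 visit and scored 3 or less would count as cured.

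**Working it through.** **Inputs.** One-sided 95% Clopper-Pearson interval and 40% null value (SAP 7.9.1); assumed cure rate 70%, 22 evaluable, 24 included (SAP 5.1). The number without a Day 7 score is not in the documents. I take 1 to 4 of 24; the plan's own allowance is 24 − 22 = 2.

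**The plan's figure.** Normal approximation: n = [(1.645·√(0.4·0.6) + 1.282·√(0.7·0.3)) / 0.3]² = 21.6, rounded up to 22. This matches. With the exact interval actually planned, power is 0.814 at n = 22 and 0.847 at n = 24. That is a separate matter, but it shows there is little slack.

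**Lower limits.** L(x, n) is the 5% quantile of Beta(x, n − x + 1).

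| Missing | Cures | Dropped | Kept as not cured |
|---|---|---|---|
| 1 | 14 | 14/23: 41.7%, success | 14/24: 39.7%, failure |
| 2 | 14 | 14/22: 43.9%, success | 14/24: 39.7%, failure |
| 3 | 13 | 13/21: 41.7%, success | 13/24: 35.8%, failure |

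The smallest successful counts are 15 at n = 24, 14 at n = 23 or 22, and 13 at n = 21 or 20.

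**How often the readings disagree.** With a 70% cure rate among observed patients, the chance of opposite verdicts is the difference in success probability, P(X ≥ threshold at 24 − k) − P(X ≥ 15), with X ~ Bin(24 − k, 0.7).
- 1 missing: 0.880 − 0.771, or 10.9%.
- 2 missing: 0.814 − 0.671, or 14.2%.
- 3 missing: 0.852 − 0.551, or 30.2%.

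**False success if the missing patients are all failures.** Let k patients be certain early failures and let the overall cure rate be 40%. The other 24 − k patients then have cure probability 9.6/(24 − k).

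| k | Dropped | Counted as not cured |
|---|---|---|
| 0 | 0.022 | 0.022 |
| 1 | 0.051 | 0.020 |
| 2 | 0.047 | 0.018 |
| 3 | 0.102 | 0.016 |
| 4 | 0.097 | 0.013 |

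If missingness is unrelated to outcome, dropping 1 to 4 patients gives 0.021 to 0.035, below the nominal 5%.

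**Antifungal case.** With 14 other cures, scoring one early antifungal user as cured gives 15/24 (43.7%, success); scoring her not cured gives 14/24 (39.7%, failure). Suppose she would otherwise have failed and has a 0.35 to 0.89 chance of scoring 3 or less. At 40% overall cure the false-success chance is then P(Bin(23, 9.6/23) + Bin(1, r) ≥ 15) = 0.031 to 0.047. That range is the span of short-term cure rates in protocol 1.1 and Table 1. It mixes uncomplicated and severe disease, includes rates measured 7–14 days after treatment, and is probably high for rescue in the first week.

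**The case against.** **The rules can be reconciled.** SAP 7.1.1 is the only text that sets a denominator, and 7.1.5 tells the analyst not to impute without telling her to exclude anyone. Cured, not cured and missing could all be reported over the FAS, and the sample-size sentence is only planning rationale. This is a fair reading, and it is close to the rule proposed below. But 7.1.1 governs percentages and does not mention the interval or the test. An analyst could equally treat 7.1.5 as the stated exception, which gives the opposite answer. The primary section has to say which.

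**No inflation at the plan's allowance.** This stands. A reader might infer that dropping early leavers breaks the 5% level, but with one or two certain failures the figure is 0.051 or 0.047. The documents give no rate of early withdrawal and do not say that leavers are failures.

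**The antifungal case is rare.** This largely stands. Antifungals are prohibited (protocol 5.7). Before Day 14 the protocol provides fluconazole only for withdrawing patients (protocol 5.2.1), and unscheduled-visit data are generally listed, not analysed (SAP 7.1.4). It would be wrong to say that the plan has an explicit rule to score rescued patients as cured; the gap comes from silence.

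**Any missing item as failure is too harsh.** This stands. With five items at 0 and one missing, the score cannot exceed 3, so she is certainly cured. The fix allows for this.

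**Readers could recompute.** Missing counts, attendance and listings are to be reported in this feasibility study, so either denominator could be rebuilt. That helps a reader, but does not settle which result is primary. The per-protocol analysis does not settle it either: it drops the patient and runs only if a relevant number are excluded.

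**Conclusion.** The point holds as a should-fix. The plan leaves it open whether a FAS patient without a Day 7 CVVS is in the primary denominator, and one such patient can turn success (14/23, 41.7%) into failure (14/24, 39.7%). The main harm is an undetermined, possibly optimistic, primary result. Type I error clearly above 5% through dropping needs three or more of 24, all certain failures (0.102 with three). Antifungal use before Day 7 is a minor addition. The limits are exact; the numbers missing and their link to outcome are assumptions.

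**What to change.** - **SAP 7.9.1 and 8.5.** State that the denominator of the cure rate and its interval is all FAS patients, and that a patient whose Day 7 cure status cannot be determined counts as not cured, as a named exception to 7.1.5.
- **Partly missing items.** Classify from the items present when status is certain: cured if the score stays at 3 or less with every missing item set to 3; not cured if the observed items already exceed 3.
- **SAP 7.9.4.** Add the observed-data analysis as a sensitivity analysis.
- **Protocol 4.4–4.6.** Ask patients who stop the pessary early to attend the scheduled Day 7 (+2 days) visit unless they withdraw consent.
- **Minor addition.** Count antifungal use before the Day 7 visit as not cured; the data are already collected (protocol 5.7, SAP 7.7).

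The cost is a few sentences and one table, with no new visit or data field. The real price is power if scores are missing at random: at 70% cure, 0.771 against 0.880 with one missing, and 0.671 against 0.814 with two. If two are true early failures and overall cure is 70% (so 16.8/22 = 76.4% in the others), it is 0.874 against 0.945. This is why early stoppers should be examined and the observed-data result shown alongside.

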#### 7.1.6 *Interim analyses*

Not applicable.

### 7.1.7 *Multiplicity*

Although there are two co-primary endpoints, no adjustment of e.g. p-values or confidence intervals will be applied. This is for two reasons, the first being that the evaluation of the second co-primary endpoint (safety and tolerability) will only be based on descriptive statistics and data listings, and the second is that both co-primary endpoints have to show favorable results.

For all other statistical analyses of the secondary endpoints, no adjustment due to multiple testing will be performed. It should be noted that the probability of making a type I error increases with the number of statistical tests performed.

### 7.1.8 *Subgroups*

Descriptive results of the primary clinical performance endpoint will be presented by study center, and by whether the patients at Day 0 reported 3 or more Vaginal Candida infections during the last 12 months or not.

## 7.2 *Analysis sets*

The decision on the classification of patients to each analysis set will be taken at the clean file meeting and documented in the clean file report together with the reasons for excluding patients from analysis sets.

### 7.2.1 *Full analysis set*

Full Analysis Set (FAS): This is the primary population and comprises all patients entering the study and having received at least 1 dose of study treatment. Analyses of clinical performance will be performed against this population.

In addition to this, two sub-populations based on this FAS will be formed: “FAS (For patients not receiving prolonged treatment)”, and “FAS (For patients receiving prolonged treatment)”.

### 7.2.2 *Per-protocol analysis sets*

Per Protocol (PP) Population 1 (PPAS Clinical Cure) - This will include all FAS patients without any major protocol deviation, i.e. patients who have completed the study and sufficiently complied with the study protocol, have available primary endpoint data and have received the study treatment according to protocol. The final definition of a major protocol deviation will be decided and defined at the clean file meeting and documented in the clean file report. If a relevant number of patients are excluded from the PP population, then the analysis of the primary clinical performance endpoint will be provided for the PP population. The main purpose with this analysis set is to analyse the primary endpoint, i.e. Clinical Cure.

Per Protocol (PP) Population 2 (PPAS Recurrence) - In addition to what was specified in the CIP, a second Per-protocol analysis set will be defined with the main purpose of analysing recurrence. The rationale for this is that the different recurrence rate analyses are regarded as important to also perform using a “per protocol” approach. The main purpose with this per protocol dataset is thus to analyse Recurrence. This population will constitute a sub-population from PP population 1 defined

above, and will be defined in similarity with this population, but instead based on the secondary recurrence rate endpoints. The final definition of a major protocol deviation with respect to these secondary endpoints, will be decided and defined at the clean file meeting and documented in the clean file report.

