5.2.1 Rescue Medication

Fluconazole will be used as rescue medication in this investigation, and patients will receive a prescription for fluconazole if considered necessary to relieve their VVC symptoms on Day 14. Patients withdrawing at any point in the investigation may receive fluconazole if considered necessary by the Investigator. The dose of fluconazole will be decided by the Investigator on an individual basis. The use of rescue medication will be recorded in the eCRF.

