5.7 Prior and Concomitant Medication

Information about any concomitant medication, including OTC medications and vitamins taken by patients during the study and within 14 days prior to inclusion shall be documented in the eCRF. The generic name or trade name, dosage, and reason for use shall be recorded for all medications.

NOTE: Antifungal medication during the study and within 14 days prior to inclusion is strictly prohibited

See [Appendix 1, Section 3](#) for specific questions.

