9.1.1 Analysis Data Sets and Populations

The two different analysis datasets that will be considered for analysis is as below:

Full Analysis Set (FAS): This is the primary population and comprises all patients entering the study and having received at least 1 dose of study treatment. Analyses of clinical performance will be performed against this population.

Per Protocol (PP) Population - This will include all FAS patients without any major protocol deviation, i.e. patients who have completed the study and sufficiently complied with the study protocol, have available primary endpoint data and have received the study treatment according to protocol. The final definition of a major protocol deviation will be decided and defined at the clean file meeting. If a relevant number of patients are excluded from the PP population, then selected outputs will be provided for the PP population.

All safety analyses will be performed against the FAS. All patients included in the FAS will be accounted for, including those who did not complete the study along with the reasons for withdrawal.

Subject disposition table presenting the number and percentage of patients reaching each study milestone will be reported. The reasons for withdrawal from the study will be tabulated.

Patients who not qualify for the FAS population will be listed.

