#### Hypotheses for the primary clinical performance endpoint

Null hypothesis: Clinical cure rate is less than or equal to 40 %.

Alternative hypothesis (one-sided): Clinical cure rate is above 40 %.

The primary clinical safety endpoint, *i.e.* safety and tolerability based on reported treatment-emergent AEs, will be analysed descriptively only, see [Section 7.10.2](#) below, and will thus not be connected to any formal hypothesis testing.

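### The per-protocol set for Day 7 cure depends on events after Day 7, which can bias the supportive cure rate in either direction

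*SAP*

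**What the plan says.** SAP 7.2.2 defines two per-protocol sets. The first, PPAS Clinical Cure, is meant mainly for the primary endpoint. It consists of full analysis set (FAS) patients without a major deviation, explained as "patients who have completed the study and sufficiently complied with the study protocol, have available primary endpoint data" and treatment received as the protocol requires. Protocol 9.1.1 also admits only "patients who have completed the study and sufficiently complied with the study protocol". Neither document defines completion, and neither limits the treatment condition to the first course. The second set, PPAS Recurrence, is a subset of the first. The final definition of a major deviation is left to the clean file meeting.

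The endpoint is measured at the Day 7 visit. The last scheduled contacts are Day 35 without prolonged treatment and Day 42 with it (Protocol 3.4). SAP 7.8 expects 4 doses without prolonged treatment and 8 with it.

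On antifungals, Protocol 5.7 states: "Antifungal medication during the study and within 14 days prior to inclusion is strictly prohibited". Protocol 5.2.1 plans fluconazole as rescue on Day 14 and adds: "Patients withdrawing at any point in the investigation may receive fluconazole if considered necessary by the Investigator". Protocol 3.6 mentions Day 14 fluconazole recipients under early withdrawal without saying whether they count as completers.

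Under SAP 7.9 the FAS analysis is the main one. The per-protocol analysis is supportive and is run only if a relevant number of patients are excluded.

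**The concern.** Available Day 7 data is already a separate membership condition, so completion adds only a requirement about what happens after the endpoint has been measured. A patient who took all four first-course doses, attended on Day 7 and has a full score would still be dropped for leaving on Day 10. Whether she leaves may depend on whether she was cured.

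Several design features make greater loss among uncured patients plausible. Under the routing in Protocol 3.1, they are the ones who take a second course and so can miss its doses, who attend the extra Day 14 visit, and who may receive the planned Day 14 fluconazole. (Protocol 3.5.5 words the trigger as symptoms still being present, so a patient with a score of 1 to 3 might also be routed there.) If planned rescue were counted as a breach of 5.7, that too would fall mainly on Day 7 failures.

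At stake is the meaning of the robustness check. A per-protocol rate selected on later events may agree or disagree with the FAS result for reasons unrelated to adherence before Day 7.

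**Working it through.** **Inputs.** Null rate 40% (SAP, hypotheses for the primary endpoint: "Null hypothesis: Clinical cure rate is less than or equal to 40" %). Assumed true rate 70%, 90% power, 22 evaluable and 24 enrolled (SAP 5.1). Exact one-sided 95% Clopper-Pearson limit (SAP 7.9.1). Dropout after Day 7 by cure status is not given, so all losses below are assumptions.

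**The plan's own figure.** The normal approximation with null and alternative variances gives

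n = [1.645·√(0.4·0.6) + 1.282·√(0.7·0.3)]² / 0.3² = 21.56, so 22.

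This reproduces the stated number. (Under the exact method, power is 81.4% at 22 and 84.7% at 24. That is a separate matter and does not affect this point.)

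**Lower limits.** For x cures among n patients, the limit is the 5% quantile of a Beta(x, n − x + 1) distribution. At n = 24 the limit exceeds 40% from 15 cures upward.

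| Full set | Limit | Assumed later loss | Per-protocol | Limit |
|---|---|---|---|---|
| 14/24 = 58.3% | 39.7% | 1 uncured | 14/23 = 60.9% | 41.7% |
| 14/24 = 58.3% | 39.7% | 1 cured | 13/23 = 56.5% | 37.5% |
| 13/24 = 54.2% | 35.8% | 3 uncured | 13/21 = 61.9% | 41.7% |
| 15/24 = 62.5% | 43.7% | 2 cured | 13/22 = 59.1% | 39.5% |

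One or two exclusions can carry the limit across 40% in either direction.

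**Expected rate.** Let p be the true Day 7 cure rate, and let d_n and d_c be the proportions of uncured and cured patients who leave after Day 7. The expected per-protocol rate is approximately

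p(1 − d_c) / [p(1 − d_c) + (1 − p)(1 − d_n)].

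For example, with p = 0.70, d_n = 0.20 and d_c = 0.05: 0.665 / (0.665 + 0.240) = 73.5%.

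| d_n | d_c | Rate if p = 70% | Rate if p = 40% |
|---|---|---|---|
| 10% | 10% | 70.0% | 40.0% |
| 10% | 0% | 72.2% | 42.6% |
| 20% | 5% | 73.5% | 44.2% |
| 30% | 5% | 76.0% | 47.5% |
| 0% | 10% | 67.7% | 37.5% |
| 5% | 20% | 66.3% | 36.0% |

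The bias is upward when d_n exceeds d_c, zero when they are equal, and downward when d_c exceeds d_n.

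**The case against.** A reader might infer that the rule inflates the per-protocol cure rate, since failures have more reason to leave. The documents do not establish this. The rule removes cured and uncured patients alike, and cured patients have reasons to drop out too. They must still answer calls on Days 14 and 35 and post a self-collected swab on Day 35. A cured patient who recurs and takes an antifungal could breach 5.7. Relapse of 13% to 26% at 30 to 35 days is cited under Protocol Table 1, though for other treatments in severe disease. Uncured patients, for their part, need not withdraw to obtain fluconazole on Day 14, because it is planned for them. Examples that drop only failures can also be made extreme. Moving from 14/24 to 14/20 (limit 49.2%) needs 4 of 10 failures and none of 14 cures to leave, while the sample size allows for only 24 − 22 = 2 non-evaluable patients in all. These arguments stand, and they rule out a claim about direction.

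It can also be said that counting planned rescue as a major deviation sets a general note above a specific rule, and that neither per-protocol definition does so. That is fair. The two sections still differ on their face, and the status of rescue patients is left open.

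Finally, no success criterion rests on the per-protocol result, and SAP 7.3 and 7.4 would make exclusions visible. This limits the consequence. The clean file meeting is a weaker defence. It settles what counts as a major deviation but does not remove the written completion condition, and in an open-label, single-arm trial the Day 7 outcomes may be known by then.

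**Conclusion.** The point holds as one of definition. A set built for a Day 7 endpoint selects on events up to Day 35 or 42, and this can bias the supportive cure rate. Upward bias is plausible but not shown; the direction depends on differential loss that the documents do not report. Over the assumed leaving rates of 0% to 30%, the expected rate at a true 70% runs from 66.3% to 76.0%. With 24 patients, one lost failure or two lost cures can change which side of 40% the limit falls on.

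The conclusion rests on reading completion literally, as reaching the last scheduled contact. The primary test is untouched. The analysis affected is supportive and conditional, although its trigger is that exclusions are numerous, which is when selection matters most. The change is worth making because it is cheap and gives the robustness check a clear meaning.

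**What to change.** In SAP 7.2.2, define PPAS Clinical Cure only by criteria up to and including the Day 7 assessment: first-course treatment as planned, no non-study antifungal before the assessment, the visit within its window, and all six score items available. Remove the completion condition from this set. Apply completion and later criteria only to PPAS Recurrence, which is already a subset of the first and so loses nothing. Define completion, and fix the list of major deviations before outcome data are reviewed.

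Make the same change in Protocol 9.1.1 or, if the protocol is not amended, record it in SAP 7.11. Protocol 5.7 and 5.2.1 must be reconciled so that the deviation status of planned fluconazole is clear; how to do so is for the sponsor.

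The cost is small wording changes to the SAP and the protocol, with no new data or patients. The per-protocol rate may move in either direction as a result.
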